The usual starting dose for Lenvatinib in DTC is 24 mg per day (Schlumberger, Tahara et al. 2015). Hypertension is one of the most common side effects seen with lenvatinib use. Hypertension and its complications are usual in catecholamine secreting tumors like paragangliomas and pheochromocytomas. Therefore, a reduced starting dose of 20 mg daily is being proposed for this trial.

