3.0 ELIGIBILITY

3.1 Inclusion Criteria

- 3.11 Age \geq 18 years.
- 3.12 Histologically or cytologically confirmed malignant secretory or non-secretory pheochromocytoma or paraganglioma that is unresectable and deemed inappropriate for alternative local regional therapeutic approaches.
- 3.13 Measurable disease as defined in [Section 11.0](#).
- 3.14 ECOG Performance Status (PS) 0, 1, or 2 ([Appendix I](#)).
- 3.15 Life expectancy $>$ 24 weeks.
- 3.16 The following laboratory values obtained \leq 14 days prior to registration.
- Absolute neutrophil count (ANC) \geq 1500/mm³
 - White blood cell (WBC) count \geq 3,000/mm³
 - Platelet count \geq 100,000/mm³
 - Hemoglobin \geq 9.0 g/dL (5.6mmol/L)
NOTE: Transfusions are not allowed \leq 7 days prior to registration
 - Total bilirubin \leq 1.5 X upper limit of normal (ULN)
(or total bilirubin \leq 3.0 X ULN with direct bilirubin \leq 1.5 X ULN in patients with well-documented Gilbert's Syndrome)
 - Aspartate transaminase (AST/SGOT) \leq 2.5 X ULN
 - Creatinine \leq 1.5 X ULN
 - Urine protein/creatinine ratio \leq 1 OR 24-hour urine protein $<$ 1.5 gram
- 3.17 Negative pregnancy test done \leq 7 days prior to registration, for women of childbearing potential only.
- 3.18 Blood pressure (BP) $<$ 150 mmHg (systolic) and $<$ 90 mmHg (diastolic). Initiation or adjustment of BP medication is permitted prior to registration provided that the average of three BP readings at a visit prior to registration is $<$ 150/90 mmHg.
- NOTE:** All patients with secretory pheochromocytoma or paraganglioma are REQUIRED to: 1) be evaluated in consultation by a hypertension specialist with specific experience in the management of hypertension in the setting of catecholamine-secreting tumors (usually an endocrinologist, nephrologist, or a cardiologist), and in the setting of hormone-associated hypertension) receive α - and β -adrenergic blockade for at least 7-14 days prior to initiation of lenvatinib (see [Appendix IV](#) for guidelines regarding proper α - and β -blockade). The hypertension specialist of record for each patient should be committed to closely following the patient during the clinical study with evaluation by said specialist required at Cycle 1 and 2 and thereafter on an as needed basis. Please see [Appendix IV](#) for guidelines on hypertension evaluation, follow up and management.
- Please note that this is a critical patient safety issue and that no exceptions to this approach are permitted.**

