4.0 STUDY CALENDAR

4.1 Test Schedule

Tests and procedures ¹				Active Treatment				End of Treatment	
	≤28 days prior to registration	≤14 days prior to registration	≤7 days prior to registration	Cycle 1			Prior to Day 1 of subsequent cycles ³	Every 2 months	
				D1	D3	D10 ²			
Tests and procedures ¹	Window:						±3 days	±7 days	±14 days
Clinical Procedures									
Vital signs, history (including personal/family history for prolonged QTc) and exam, weight, PS		X		X	X	X	X		X
Height		X							
Review of concurrent medications ⁴		X					X		
Pregnancy test ⁵			X						
Blood pressure monitoring ⁶		X		X	X	X	X		
Adverse event assessment		X		X	X	X	X		X
Consultation with endocrinologist, cardiologist, or nephrologist for blood pressure management		X					X		
Hematology: CBC/diff ⁷		X					X		X
Chemistry Panel ⁸		X					X		X
TSH		X					X		
24 hr urine catecholamine and metanephhrines		X					X		
Plasma fractionated metanephhrines		X					X		
Urinalysis ⁹		X					X		
Urine protein/creatinine ratio		X					X		
Genetic counseling and testing at discretion of patient and counselor ¹⁰	X								

¹ All tests and procedures are clinically indicated, unless noted with an R to indicate funding by research

² May be omitted at discretion of treating provider and replaced with telephone call contact.

³ If patient is tolerating treatment well, return visits may be performed over the phone for non-imaging cycles (starting with cycle 3, 5, 7 etc.). During these phone visits the patient status, treatment information, and Adverse Event Assessments must be assessed and recorded. Labs may be done locally and transmitted to Mayo Clinic.

⁴ Concurrent/concomitant medications are reviewed every cycle. Only requested medications are recorded in the study case report forms.

⁵ For women of childbearing potential only. Must be done ≤7 days prior to registration

⁶ Note: 1) daily monitoring of blood pressure is REQUIRED and must be recorded in patient diaries throughout the entire duration of therapy; 2) any systolic BP >150 mm Hg and/or diastolic BP >100 mm Hg must be brought to the attention of treating provider <24h after noted; 3) any systolic BP >200 mm Hg and/or diastolic BP >110 mm HG should prompt immediate cessation of lenvatinib therapy maintained until remediation to <150 mm Hg systolic is accomplished.

⁷ Must include: hemoglobin (hgb), MCV, leukocyte count, neutrophils (ANC), monocyte count, lymphocyte count, and platelet count (PLT)

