⁸ AST, alk phos, total bilirubin (direct if TBili is elevated), creatinine (and calculated creatinine clearance), albumin, glucose, calcium (Ca), sodium (Na), potassium (K), magnesium (Mg), phosphorus (P), uric acid, LDH,

⁹ Urinalysis for protein, glucose, blood

¹⁰ Only if not performed previously (optional); can be performed anytime during study. Testing should include SDHD, SDHB, RET, VHL, neurofibromatosis type-1 genes.

Tests and procedures ¹	Window:				Active Treatment			End of Treatment
		≤28 days prior to registration	≤14 days prior to registration	≤7 days prior to registration	Cycle 1		Prior to Day 1 of subsequent cycles ³	
		D1	D3	D10 ²	Every 2 months			
PET-CT or CT (Chest, Abdomen and pelvis), or MRI abdomen/MRI neck, if needed	X						X	X ¹¹
ECG		X					X ¹²	
2D-ECHO	X							
Blood or Tissue- Analysis performed by Research Lab								
Optional tissue sample for correlatives (see Section 17.0) ¹³				X				
Optional research blood will be collected under IRB 13-005838 ¹⁴		X						
Quality of Life assessment								
Patient Questionnaire Booklet: EQ-5D-5L/FACT-G				X ¹⁵			X	

Cycle = 28 days

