6.8 Baseline symptoms

All required baseline symptoms (see Section 10.0) must be documented and graded.

6.9a Study drug availability

Study drug is available on site for this patient.

6.9b Booklet availability

Patient questionnaire booklet is available on site for this patient; copies are not acceptable for this submission.

6.9c Consultation with hypertension specialist

A hypertension specialist (endocrinologist, or cardiologist, or nephrologist) at enrolling institution has seen this patient and confirms the patient is a suitable candidate for this study ≤ 14 days prior to registration.

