7.0 PROTOCOL TREATMENT

7.1 Treatment Schedule

Treatment will be administered on an outpatient basis. Reported AEs and potential risks are described in Sections 9 and 10. No other investigational or commercial agents or therapies may be administered with the intent to treat the subject's malignancy.

Subjects will receive lenvatinib on an outpatient basis at a dose of 20 mg/day (two 10-mg capsules; dose modification will be accomplished by combining 10-mg and 4-mg capsules as necessary). Subjects are instructed to swallow capsules once a day (preferably in the morning) with or without food with about 1 cup (240 mL) water. Capsules should be swallowed whole; they must not be chewed, broken, or crushed. Treatment continues until progression, excessive toxicity, or patient refuses to continue study medication. Missed and/or withheld doses of lenvatinib (whether intentional or not) are to be reported in the Medication Diary, but not made up.

- Patients will be provided with a Medication Diary for lenvatinib (Appendix II). Patient should bring the diary back at the end of each cycle of treatment.
- Any blood pressure medications patients is already taking or started during the treatment period should be listed in the CRF.

Study drug lenvatinib will be administered at a dose of 20 mg daily by mouth on a 28 day cycle for a maximum of 5 years.

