8.1 Dose Modification Table

If patient is able to tolerate the starting dose of 20 mg daily for the first 2 cycles and if patient shows stable disease (SD) or objective response (OR) by RECIST 1.1 (see Section 11.0), then dose can be escalated to 24 mg daily at the physician's discretion.

Otherwise follow the dose modifications below:

Dose Level	Lenvatinib
+1	24 mg daily
0*	20 mg daily
-1	14 mg daily
-2	10 mg daily

*Dose level 0 refers to the starting dose.

ALERT: ADR reporting may be required for some adverse events (See Section 10.0)

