- Distribution:** In vitro binding of lenvatinib to human plasma proteins is high and ranged from 98% to 99% (0.3 – 30 μ g/mL, mesilate). This binding was mainly to albumin with minor binding to α 1-acid glycoprotein and γ -globulin. In vitro blood to plasma ratios of lenvatinib (0.1 - 10 μ g/mL) remained constant in humans (0.589 – 0.608).
- Metabolism:** Lenvatinib is extensively metabolized in humans. The main metabolic pathways in humans were identified as oxidation by AO, demethylation via CYP3A4, glutathione conjugation with elimination of the O-aryl group (chlorbenzyl moiety), and combinations of these pathways followed by further biotransformations (eg, glucuronidation, hydrolysis of the glutathione moiety, degradation of the cysteine moiety, and intramolecular rearrangement of the cysteinylglycine and cysteine conjugates with subsequent dimerization).
- Half-life elimination:** Plasma concentrations decline bi-exponentially following C_{max} . The terminal exponential half-life of lenvatinib is about 28 hours.

Excretion: Following administration of radiolabeled lenvatinib to 6 subjects with solid tumors, approximately two-thirds and one-fourth of the radiolabel were eliminated in the feces and urine, respectively.

Special populations: No dose adjustments are required on the basis of hepatic function in patients with mild (Child-Pugh A) or moderate (Child-Pugh B) hepatic impairment. In patients with severe

(Child Pugh C) hepatic impairment, the starting dose should be lowered. No dose adjustments are required on the basis of renal function in patients with mild or moderate renal impairment. In patients with severe renal impairment, the starting dose should be lowered. Further dose adjustments may be necessary on the basis of individual tolerability.

15.16 **Potential Drug Interactions:** In vitro, cytochrome P450 3A4 was the predominant (>80%) cytochrome isoform involved in the P450-mediated metabolism of lenvatinib. In vivo, inducers and inhibitors of CYP3A4 had a minimal effect on lenvatinib exposure. Lenvatinib is not considered a strong inducer or inhibitor of cytochrome P450 or uridine 5'-diphospho-glucuronosyl transferase (UGT) enzymes. Lenvatinib may be co-administered without dose adjustment with CYP3A, P-glycoprotein (P-gp), and BCRP inhibitors or CYP3A and P-gp inducers.

15.17 **Known potential adverse events:**

Common known potential toxicities, >10%:

Gastrointestinal disorders: Abdominal pain, diarrhea, nausea, vomiting

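### Section 15.15 asks for a lower starting dose in severe renal impairment, but Sections 7.1, 7.11 and 8.1 start every patient at 20 mg and Section 3.16 sets no creatinine clearance floor

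*Combined protocol and SAP*

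**What the plan says.** All references are to the combined protocol and SAP.

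- **Section 15.15, special populations.** Mild or moderate renal impairment needs no adjustment. Then: "In patients with severe renal impairment, the starting dose should be lowered". No dose, clearance cut-off or definition of severe is given.
- **Section 7.1.** "Subjects will receive lenvatinib on an outpatient basis at a dose of 20 mg/day". The table in 7.11 repeats 20 mg daily. No renal exception appears in either place.
- **Section 8.1.** "Dose level 0 refers to the starting dose", and level 0 is 20 mg. The levels of 14 mg and 10 mg are reductions.
- **Section 1.3.** The usual start in differentiated thyroid cancer is 24 mg. The text cites the hypertension risk of the drug and of catecholamine-secreting tumors, and concludes: "Therefore, a reduced starting dose of 20 mg daily is being proposed for this trial".
- **Section 3.16.** The renal limits are "Creatinine \leq 1.5 X ULN" and a proteinuria limit. Section 3.11 sets no upper age limit, Section 3 sets no weight limit, and Section 3.2 lists no renal exclusion.
- **Section 4.1, footnote 8.** The chemistry panel, due within 14 days before registration, covers "creatinine (and calculated creatinine clearance" among its items. No equation is named, and no eligibility or dosing rule uses the value.
- **Section 6.9c.** A hypertension specialist "confirms the patient is a suitable candidate for this study". No renal criterion is attached.

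**The concern.** For a patient who is eligible on creatinine but has severe renal impairment, the treatment sections say 20 mg and the drug section says to go lower by an unstated amount. Section 8.0 asks for strict adherence to the modification table in the first two cycles. Sections 8.2 and 8.3 and Appendix IV reach lower levels only after an event on treatment, so no text assigns a lower level at baseline.

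The stake is one patient's first dose, and whether two clinicians would choose the same one. Section 15.17 lists acute kidney injury and hypertension among the common toxicities of this drug. The protocol already has the clearance that would settle the matter calculated at screening, and then does not use it.

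**Working it through.** **Step 1. Can 20 mg be read as the lowered dose?** Section 1.3 applies 20 mg to all patients because of hypertension, and 8.1 calls it the starting level. So 20 mg is not itself a renal reduction, although 15.15 does not say which starting dose it has in mind.

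**Step 2. Can an eligible patient have severe impairment?** The only input from the documents is the ceiling of 1.5 × ULN. The following are assumptions, because the documents give none of them: the Cockcroft-Gault equation, severe meaning clearance below 30 mL/min, and a ULN of 0.9 to 1.2 mg/dL (women) or 1.1 to 1.3 mg/dL (men).

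Clearance = (140 − age) × weight ÷ (72 × creatinine), times 0.85 for women. At the ceiling, creatinine is 1.35 to 1.80 (women) or 1.65 to 1.95 (men).

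| Patient | Numerator | Low ULN | High ULN |
|---|---|---|---|
| Woman, 80 y, 45 kg | 60 × 45 × 0.85 = 2295 | 2295 ÷ 97.2 = 23.6 | 2295 ÷ 129.6 = 17.7 |
| Woman, 70 y, 50 kg | 70 × 50 × 0.85 = 2975 | 2975 ÷ 97.2 = 30.6 | 2975 ÷ 129.6 = 23.0 |
| Man, 80 y, 60 kg | 60 × 60 = 3600 | 3600 ÷ 118.8 = 30.3 | 3600 ÷ 140.4 = 25.6 |
| Woman, 50 y, 70 kg | 90 × 70 × 0.85 = 5355 | 5355 ÷ 97.2 = 55.1 | 5355 ÷ 129.6 = 41.3 |
| Man, 55 y, 80 kg | 85 × 80 = 6800 | 6800 ÷ 118.8 = 57.2 | 6800 ÷ 140.4 = 48.4 |

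The first patient is severe across the assumed ULN range. The next two are severe at the high ULN and just above 30 at the low one. The last two, of more ordinary age and weight, are never severe.

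**Step 3. How fragile is that?**

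- *Creatinine below the ceiling.* At 1.2 × ULN each value rises by 1.5 ÷ 1.2 = 1.25. The first three patients become 29.5/22.1, 38.3/28.7 and 37.9/32.1. The man is no longer severe.
- *Another equation.* CKD-EPI (assumed 2021 form, indexed to body surface) is 142 × (creatinine ÷ κ)^−1.2 × 0.9938^age, times 1.012 for women, with κ of 0.7 (women) or 0.9 (men), for creatinine above κ. At 1.5 × ULN the first three patients read 39.7/28.1, 42.3/29.9 and 41.7/34.1. Only the two women fall below 30, and only at a ULN of 1.2.

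The 80-year-old woman reads 17.7 to 23.6 by one equation and 28.1 to 39.7 by the other. A rule based on clearance must therefore name its equation.

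**Step 4. Dose at stake.** If the reduced start were level −1 (14 mg, an assumption), a 28-day cycle would be 28 × 14 = 392 mg against 28 × 20 = 560 mg, or 70%.

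**Step 5. The trial's design figures.** The design declares promise with at least 1 response in 6 and at least 4 in 23. The probability is the sum over x = 1 to 6 of b(x; 6, p) × P(Bin(17, p) ≥ 4 − x). This gives 0.149 at p = 0.10 and 0.852 at p = 0.30, with early stopping of 0.9^6 = 0.53 and 0.7^6 = 0.12. These match the table in Section 16.13 and use no renal input.

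**The case against.** **Section 15 is general drug reference.** It allows capsules to be dispersed in liquid (15.14) where 7.1 requires them whole, and 15.192 mentions immunotherapy given at the same time, although 7.1 bars other agents aimed at the malignancy. On this view the starting dose in 15.15 may be the general 24 mg. This partly stands: a contradiction aimed specifically at this trial's 20 mg is an inference. But 15.15 is dosing advice printed in the protocol, and nothing tells the clinician to disregard it.

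**Safeguards exist.** The specialist signs off suitability (6.9c) when screening clearance is being obtained. Section 9.74 plans electrolytes and clinic visits on Days 1, 3 and 10, and 15.199 asks for renal function to be monitored. Section 8.2 holds and reduces after other Grade 3 non-hematologic events. All of this stands. A reader might infer from the calendar, where the next chemistry panel falls before Cycle 2, that the first cycle runs unwatched. Sections 9.74 and 15.199 do not support that. Even so, 9.74 does not name creatinine, and none of these provisions sets a starting dose.

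**Reachability is assumed.** The equation, cut-off and ULN are all from outside the documents, which give no age or weight distribution. This stands, and it is why the case is described as rare.

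**Conclusion.** The conflict is real and minor. Following 7.1 as written gives a rare eligible patient a first dose that the protocol's own drug section says should be lower. Existence of the conflict rests on the text alone. That an eligible patient can meet it rests mainly on Cockcroft-Gault with a 30 mL/min cut-off, in an older, light patient near the creatinine limit. With CKD-EPI it nearly vanishes. "Few if any" of 23 to 25 patients is a judgement, since the documents allow no count.

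Two stronger readings are not supported. A reader might infer that such a patient has no dosing rule, but there is a clear one (20 mg) and the problem is that 15.15 disagrees with it. A reader might also infer that 15.15 calls for 14 mg, but it names no dose. Sample size, error rates and the primary analysis are unaffected.

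**What to change.** **Preferred.** Add to Section 3.16 a calculated creatinine clearance of at least 30 mL/min, and name the equation in footnote 8 of Section 4.1 (for example Cockcroft-Gault). The cut-off is an assumption for the sponsor to confirm. No new test is needed. The cost is amendment wording and the loss of a rare candidate in a disease expected to accrue 4 to 8 patients per year.

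**Alternative.** State in 7.1, 7.11 and 8.1 a reduced start for patients below the cut-off, for example level −1 (14 mg). That dose is also an assumption for the sponsor to confirm. Say that 10 mg is then the only tabulated reduction left, and whether the escalation in 8.1 applies to them. The cost is that such a patient starts at 70% of the studied dose and still counts in the response rate.

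The neighbouring sentence in 15.15 on Child-Pugh C also names no dose. The same amendment could settle it, though whether such a patient could be eligible was not examined here.

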16.0 STATISTICAL CONSIDERATIONS AND METHODOLOGY

16.1 Statistical Design:

A Simon two-stage, phase II optimal clinical trial design was chosen to examine anti-tumor activity and safety profile of lenvatinib as a treatment for patients with progressive malignant pheochromocytoma or paraganglioma.

16.11 Primary endpoint

The primary endpoint is the confirmed tumor response rate defined as 100% times the number of eligible patients who has started lenvatinib and whose objective tumor status was a CR or PR on 2 consecutive evaluations at least 4 weeks apart (using RECIST v1.1 criteria) divided by the number of eligible patients who has started lenvatinib.

16.12 Operating Characteristics

The largest tumor response rate for which there would be little interest in pursuing further studies of this lenvatinib regimen in patients with progressive malignant pheochromocytoma or paraganglioma is 10%. The smallest tumor response rate for which there would be interest in pursuing further studies of this lenvatinib regimen in patients with progressive malignant pheochromocytoma or paraganglioma is 30%. The study design proposed below yields a 85% chance of detecting that the true tumor response rate is at least 30% at a 0.15 significance level when the true tumor response rate is at least 10%

16.121 Stage 1: Enter 6 eligible patients. If no tumor responses are documented among these 6 patients within the first 6 cycle of treatment, we will consider the regimen lacking in sufficient antitumor activity to recommend further testing in this patient population and terminate further enrollment. If at least one response is observed among these 6 patients within the first 6 cycles of treatment, we will proceed to Stage 2.

16.122 Stage 2: Enter an additional 17 eligible patients. If three or fewer tumor responses are documented among all 23 eligible patients within the first 6 cycle of treatment, we will consider the regimen lacking in sufficient antitumor activity to recommend further testing in this patient population. If four or more tumor responses are documented among all 23 eligible patients within the first 6 cycle of treatment, this will be considered of the regimen to have promising antitumor activity in this patient population.

We anticipate enrolling a minimum of 6 and a maximum 23 eligible. At the close of stage 1 or stage 2 enrollment, if more patients than planned have been enrolled only the first 6 eligible patients or the first 23 eligible patients enrolled, respectively, will be used to evaluate the decision rule. We anticipate accruing 2 additional patients (25 total) to account for patients found to be ineligible after signing a consent or who refused to start study treatment after signing a consent form.

16.13 Power and Significance Level

Assuming that the number of tumor responses is binomially distributed, the probability of declaring that this regimen warrants further studies (i.e. statistical power) under various tumor response rates and the probability of stopping

accrual after the first stage can be tabulated as a function of the true tumor response rates as shown in the following table.

If the true tumor response rate is	10%	15%	20%	25%	30%
Then the probability of declaring that the regimen warrants further study is...	0.15	0.37	0.59	0.75	0.85
And the probability of stopping at the completion of stage 1	0.53	0.38	0.26	0.18	0.12

16.14 Accrual Time and Study Duration:

No similar studies have been conducted for comparison. Based on our anecdotal experience from referrals of patients from outside institutions who would otherwise fit eligibility criteria we believe we will be able to enroll 4 to 8 patients per year at our institution (Mayo clinic). We believe we can complete accrual within the proposed 3-year period.

16.2 Analysis Plan:

16.21 Primary Endpoint:

Ninety-five percent confidence intervals for the true response proportion will be calculated according to the approach of Duffy and Santner (Duffy and Santner 1987).

